9.5.9 Clinical Safety Laboratory Assessments

Refer to Appendix 2 for the list of clinical laboratory tests to be performed and to the SoA for the timing and frequency.

- The investigator must review the laboratory report, document this review, and record any clinically relevant changes occurring during the study in the AE section of the CRF. The laboratory reports must be filed with the source documents. Clinically significant abnormal laboratory findings are those which are not associated with the underlying disease, unless judged by the investigator to be more severe than expected for the participant's condition.
- All protocol-required laboratory assessments, as defined in Appendix 2, must be conducted in accordance with the laboratory manual and the SoA.
- If laboratory values from non-protocol specified laboratory assessments performed at the institution's local laboratory require a change in study participant management or are considered clinically significant by the investigator (eg, SAE or AE or dose modification), then the results must be recorded in the appropriate CRF (eg, SLAB).
- For any laboratory tests with values considered clinically significantly abnormal during participation in the study or within 30 days after the last dose of study treatment, every attempt should be made to perform repeat assessments until the values return to normal or baseline or if a new baseline is established as determined by the investigator.

Details regarding specific laboratory procedures/assessments to be performed in this study are provided below. The total amount of blood/tissue to be drawn/collected over the course of the study (from pre-study to post-study visits), including approximate blood/tissue volumes drawn/collected by visit and by sample type per participant can be found in the Study Vendor Manual. Refer to the Schedule of Activities (Section 2) for the timing of laboratory assessments.

Only safety labs affecting potential treatment must be reviewed prior to study therapy administration following the Screening Visit. Labs that would not affect potential treatment of the participant can be reviewed, in a timely manner, by an investigator after the date of study therapy administration. Similarly, if a site is unable to obtain the thyroid function testing (thyroid stimulating hormone [TSH], Free T3 and Free T4) results prior to scheduled dosing, review of the thyroid function test results after dosing is acceptable and poses no additional immediate safety risk to participants.

9.5.9.1 Laboratory Safety Evaluations (Hematology, Chemistry, and Urinalysis)

Laboratory tests for hematology, chemistry, and urinalysis are specified in Appendix 2. All laboratory tests to determine eligibility and Drug-Induced Liver Injury (DILI) (see Section 5.1 – Entry Criteria [[Table 1](#)] and Section 9.3.7 – Events of Clinical Interest, respectively) are mandatory; all other additional laboratory tests are recommended and may be performed according to local institutional standard.

9.5.9.2 Pregnancy Test

- Pregnancy testing for WOCBP:
 - Pregnancy testing requirements for study inclusion are described in Section 6.1.
 - Pregnancy test is required to be repeated within 24 hours prior to starting RT ± cisplatin adjuvant treatment.
 - Pregnancy testing (urine or serum as required by local regulations) should be conducted at monthly intervals during intervention and at the end of treatment.
 - Pregnancy testing (urine or serum as required by local regulations) should be conducted for the time required to eliminate systemic exposure after the last dose of each study intervention(s) as noted in Section 6.1. The length of time required to continue pregnancy testing for each study intervention is as follows:
 - Pembrolizumab: 120 days
 - Cisplatin: 180 days
 - Radiotherapy: 180 days
 - Additional serum or urine pregnancy tests may be performed, as determined necessary by the investigator or required by local regulation, to establish the absence of pregnancy at any time during the participant's participation in the study. Refer to Appendix 8 for UK-, Germany-, and France-specific requirements.

9.5.9.3 HIV, HBV and HCV Serology

Screening tests are not required unless mandated by local regulations. HIV, HBV, and HCV serology will be conducted on participants per local regulations and site SOPs. Active Hepatitis B is defined as a known positive HBsAg result. Active Hepatitis C is defined by a known positive Hep C Ab result and known HCV RNA results greater than the lower limits of detection of the assay. Refer to Appendix 8 for Germany-specific requirements for HIV, HBV, and HCV testing.

9.6 Pharmacokinetics

Pharmacokinetic samples are not collected in this trial.

9.6.1 Blood Collection for RNA Analysis and Plasma and Serum Biomarker Analyses

Blood should be drawn according to the collection schedule for all participants (Section 2.0). Leftover RNA, plasma, and serum will be stored at the end of the study for FBR if the participant has consented (see Section 9.8). Further details are provided in the Vendor Manual.

9.7 Pharmacodynamics

Pharmacodynamic parameters will not be evaluated in this study.

9.8 Future Biomedical Research Sample Collection

The following specimens are to be obtained as part of Future Biomedical Research:

- DNA for future research
- Leftover RNA from RNA analyses
- Leftover plasma from plasma biomarker analyses
- Leftover serum from serum biomarker analyses
- Leftover plasma from ctDNA
- Leftover main study tumor

9.9 Biomarkers

Collection of samples for other biomarker research is also part of this study. The following samples for biomarker research are required and will be collected from all participants in this study as specified in the SoA:

- Blood for Genetic Analysis
- Blood for RNA Analysis

- Blood for Serum Biomarker Analysis
- Blood for Plasma Biomarker Analysis
- Blood for ctDNA Analysis
- Tissue Collection for Biomarker Analysis

9.9.1 Planned Genetic Analysis Sample Collection

The planned genetic analysis sample should be obtained pre-dose on Day 1 but may be collected at the next scheduled blood draw, if needed. Sample collection, storage and shipment instructions for planned genetic analysis samples will be provided in the Vendor Manual. Samples should be collected for planned analysis of associations between genetic variants in germline/tumor DNA and drug response. If a documented law or regulation prohibits (or local IRB/Independent Ethics Committee [IEC] does not approve) sample collection for these purposes, then such samples should not be collected at the corresponding sites. Leftover DNA extracted from planned genetic analysis samples will be stored for FBR only if participant provides documented informed consent for FBR.

9.10 Visit Requirements

Visit requirements are outlined in Section 2 – Schedule of Activities (SoA). Specific procedure-related details are provided above in Section 9 – Study Assessments and Procedures.

9.10.1 Screening

Approximately 28 days prior to treatment randomization, potential participants will be evaluated to determine that they fulfill the entry requirements as set forth in Section 6.1. Screening procedures may be repeated after consultation with the Sponsor.

Documented informed consent must be obtained prior to performing any protocol-specific procedure. Results of a test performed prior to the participant providing consent as part of routine clinical management are acceptable in lieu of a screening test if performed within the specified time frame. Screening procedures are to be completed within 28 days prior randomization except for the following:

- Laboratory tests are to be performed within 10 days prior to randomization. An exception is hepatitis testing which may be done up to 28 days prior to randomization.
- Evaluation of ECOG performance status is to be performed within 10 days prior to randomization.
- For WOCBP, a urine or serum pregnancy test will be performed within 24 hours (urine) or within 72 hours (serum) before randomization. If urine pregnancy results cannot be confirmed as negative, a serum pregnancy test will be required (performed by the local study site laboratory).

- For cases where newly obtained tumor sample is collected within 90 days of randomization, tumor sample collection is not required to be obtained within 28 days prior to randomization for PD-L1 testing for all participants and for HPV p16 testing for participants with oropharyngeal cancers.

Participants may be rescreened after initially failing to meet the inclusion/exclusion criteria after consultation with the Sponsor. Results from assessments during the initial screening period are acceptable in lieu of a repeat screening test if performed within the specified time frame and the corresponding inclusion/exclusion criteria is met. Participants who are rescreened will retain their original screening number.

After screening, eligible participants will be randomly assigned to treatment. Sites will contact the participants to advise them on their assigned treatment arm and schedule the first post-screening visit as determined by their assigned treatment arm.

9.10.2 Treatment Periods

Visit requirements are outlined in the Schedule of Activities (Section 2.0). Specific procedure-related details are provided in Section 9.1.

In the Neoadjuvant Treatment Phase, there are 2 treatment arms: Arm A/pembrolizumab and Arm B/SoC (no neoadjuvant). Post-definitive surgery, participants will receive adjuvant treatment with RT \pm cisplatin plus pembrolizumab in Arm A and without pembrolizumab in SoC arm (Arm B), as assigned during randomization. No crossover from SoC to pembrolizumab will be permitted. Participants who subsequently receive any anticancer treatment not specified in the protocol will discontinue study treatment and enter Follow-up; any treatment would be considered post-study anticancer treatment.

9.10.2.1 Neoadjuvant Treatment (Treatment 1)

Only participants in Treatment Arm A/pembrolizumab will receive neoadjuvant pembrolizumab; participants in Treatment Arm A/pembrolizumab should proceed to surgery directly following the presurgery visit (within 6 weeks [\pm 10 days]) after randomization). Participants in Arm A are allowed to go to surgery outside this timeframe if delays are due to an AE. Participants with delays other than for an AE may be considered with sponsor consultation. Participants in the Treatment Arm B/SoC will proceed directly to surgery following within 4 weeks after randomization.

Visit timing requirements during the treatment period for Arm A are as follows:

- Assessments/procedures should be performed on Day 1 for each cycle.
- Pembrolizumab treatment cycles are 3 weeks (21 days).
- The window for each visit is \pm 3 days, unless otherwise noted. Cycle 1 treatment should begin within 3 days of randomization or as close as possible to that date on which the participant is allocated or assigned.

9.10.2.2 Definitive Surgery

All participants will have presurgical assessments performed at Week 0-4 (\pm 10 days) for the SoC arm (Arm B) or Week 6 (\pm 10 days) for the pembrolizumab arm (Arm A), to allow assessment of disease status, PROs and safety monitoring. The window for this visit allows participants to proceed to surgery up to 10 days earlier or later if deemed necessary by the investigator.

Definitive surgery will be performed as per local SoC (Arm B/SoC) and following completion of neoadjuvant treatment (Arm A/pembrolizumab). Note: Participants in the pembrolizumab arm (Arm A) may proceed to surgery after 1 dose of pembrolizumab, if deemed appropriate, if the investigator has documented clinical evidence of tumor progression, preferably supported by radiographic evidence.

Participants who do not undergo surgery as originally planned may proceed directly to Treatment 2 and receive salvage RT plus cisplatin \pm pembrolizumab, depending on treatment assignment at the discretion of the investigator in consultation with the Sponsor.

9.10.2.3 Post-surgery Safety Follow-up

The mandatory Post-surgery Safety Follow-up Visit should be conducted approximately 7 to 30 days post-surgery. All AEs that occur post-surgery and prior to the Post-surgery Safety Follow-up Visit should be recorded. Section 9.3.1 details the reporting requirements for AEs and SAEs considered to be post-surgical complications by the investigator. Complications and mortality as a consequence of the surgical procedures will be reported as per other AEs and SAEs (see Section 9.1.10.2.3).

Participants considered to have adequately recovered from surgery may proceed directly to adjuvant treatment.

9.10.2.4 Adjuvant Treatment (Treatment 2)

The post-surgery adjuvant treatment period (Treatment 2) is expected to start when participants have recovered adequately from the morbidity and/or complications from the surgery and with RT \pm cisplatin commencing at a recommended minimum range of within 6 weeks after definitive surgery. If performed outside of this window, Sponsor consultation will be required. If the start of RT is delayed, up to 4 doses of pembrolizumab may be given. The timing of this dose of pembrolizumab can be adjusted based on timing of surgery after discussion with the Sponsor. The first dose of pembrolizumab given during radiation therapy should be given such that pembrolizumab continues to be given every 21 \pm 3 days.

9.10.3 Post-Treatment Visit

Post-treatment visit requirements are outlined in the Schedule of Activities (Section 2.4).

9.10.3.1 End of Treatment Visit

The End of Treatment visit should occur at the time study treatment is discontinued for any reason. If the End of Treatment visit occurs 30 days from the last dose of study treatment, at the same time as the mandatory 30-Day Safety Follow-up visit, the End of Treatment visit procedures and any additional Safety Follow-up procedures can be combined into a single visit.

Participants who discontinue study treatment for a reason other than disease progression will still be considered on study and should continue with regularly scheduled assessments (also refer to Section 8.1), including collecting participant information on the start of new anticancer therapy, disease progression, and death.

9.10.3.2 Safety Follow-up Visit

The mandatory Safety Follow-up Visit should be conducted approximately 30 days after the last dose of study treatment or before the initiation of a new anticancer treatment, whichever comes first.

Reporting requirement for post-treatment follow-up of treatment-related late toxicities meeting serious criteria is detailed in Section 9.3.1.

9.10.3.3 Follow-up Visits

Participants who complete study treatment or discontinue study treatment for a reason other than an event/disease progression/recurrence will move into the Post-Treatment Follow-up Phase and should be assessed in office every 3 months (91 ± 7 days) until the end of Year 3 (measured from the date randomization) to monitor disease status. In Years 4 and 5, participants should be assessed in office every 6 months (182 ± 14 days) to monitor disease status. After Year 5, participants will move into Survival Follow-up. Any additional tests/investigations or imaging assessments for progressive/recurrent disease or safety will be at the discretion of participant's treating physician per local SoC. Every effort should be made to collect information regarding disease status until an event/disease progression, death, withdrawal of consent or end of study. Information regarding post-study anticancer treatment will be collected if new treatment is initiated. Participants who have completed all efficacy assessments must enter Survival Follow-up. Participants who discontinue efficacy assessments early, and have not experienced an event/progression, will be requested for standard of care imaging assessments/biopsy to evaluate disease status.

For a participant who dies during the Follow-up period, date and cause of death should be recorded in the appropriate eCRF.

Participants in Post-Treatment Follow-up will be followed for treatment-related late toxicities for up to Year 5 and should be recorded.

9.10.3.4 Survival Follow-up

All participants who complete Post-Treatment Follow-up, experience an event or disease progression/recurrence verified by BICR will move into the Survival Follow-up Phase and should be contacted by telephone every 3 months (91 ± 14 days) to assess for survival status until death, withdrawal of consent, or the end of the study, whichever occurs first.

The first survival follow-up assessment should be scheduled as described below:

- For participants who discontinue study treatment and who will not enter the Post-Treatment Follow-up Phase, the first survival follow-up contact will be scheduled 3 months (91 ± 14 days) after the End of Treatment Visit and/or Safety Follow-up Visit (whichever is last).
- For participants who completed assessments in the Post-Treatment Follow-up Phase, the first survival follow-up contact will be scheduled 3 months (91 ± 14 days) after the last efficacy assessment follow-up visit has been performed.

The Sponsor may request survival status to be assessed at additional time points during the course of the study. For example, survival status may be requested prior to the eDMC safety review, efficacy IAs and final analysis. All participants who are in the Survival Follow-up Phase and not known to have died prior to the request for these additional survival status time points will be contacted at that time.

9.10.4 Participants Discontinued From Study Treatment but Continuing to be Monitored in the Study

Participants who discontinue study treatment for reasons other than an event/disease progression/recurrence will enter Safety and Post-Treatment Follow-up and undergo all assessments at the scheduled time points are per the Schedule of Activities (Section 2.4) as described in Sections 9.10.3.2, 9.10.3.3 and 9.10.3.4.

Participants that discontinue study treatment due to an event/disease progression/recurrence will enter Safety Follow-up and then proceed directly to Survival Follow-up as described in Section 9.10.3.4 (refer to Sec 8.1 – Discontinuation of Study Treatment). Participants who discontinue study treatment because of the start of new anticancer treatment will enter Safety Follow-up and then proceed directly to Follow-up as described in Section 9.10.3.3.

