CT/MRI head and neck, chest, upper abdomen			X	X		*[X]	
For all imaging, the clock will start at the end of RT ± cisplatin. Imaging to be performed 12 weeks (± 7 days) after end of RT ± cisplatin treatment and then every 3 months (91 ± 7 days) until the end of Year 3; then every 6 months (182 ± 14 days) thereafter up to the end of Year 5. Imaging timing should follow calendar days and should not be recalculated based on the date of previous scans. The upper abdominal CT/MRI should cover the liver in its entirety.
 
Continuation of imaging/biopsies is strongly recommended for participants who have not yet experienced an event/progression and have started a new anticancer treatment.
 
*Additionally, imaging assessment/biopsies performed as part of SOC to evaluate disease status for participants in survival follow-up who have not yet experienced an event/progression should be collected during survival follow-up. All available images should be submitted to the central imaging vendor and recorded in the applicable eCRF.

End of Treatment and Follow-up Visits (Arms A and B)							
Study Period	End of Treatment	Post-Treatment Follow-up ^a				Notes	
Visit Number/Title	Discontinuation	Safety FU	Post-Treatment FU		Survival FU		
Treatment Cycle/Day			Up to end of Year 3	Years 4-5			
Scheduling Window (Days (unless noted)	At time of Treatment Discontinuation	30 days from last dose +14 days	Every 3 months from last scan ±7 days	Q6M ±14 days	Q12M ±14 days	Every 3 months ±14 days	
EQ-5D-5L	X	X	X	X			To be administered 12 weeks after end of RT ± cisplatin treatment and then every 3 months (91 ± 7 days) until end of Year 3; then every 12 months (365 ± 14 days) thereafter up to the end of Year 5.
EORTC QLQ-C30	X	X	X	X			PROs are to be administered by trained site personnel. It is strongly recommended that PROs are completed by participants prior to all procedures/assessments, and in the following order: EQ-5D-5L, EORTC QLQ-C30, EORTC QLQ-H&N35.
EORTC QLQ-H&N35	X	X	X	X			If the participant does not complete the PROs for any reason, the Miss Mode form must be completed to capture the reason the assessment was not performed.
Safety Procedures							
Full physical examination	X						To be performed by the investigator or qualified designee.
Directed physical examination		X	X	X			To include neurological exam if clinically indicated
ECOG Performance Status	X	X	X	X			

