Adjuvant treatment will start when participants have recovered adequately from the morbidity and/or complications from the surgery and is recommended within 6 weeks of surgery. For adjuvant treatment, participants considered high-risk for recurrence (ie, positive margins [< 1 mm] or extranodal extension [defined as extension of SCC from within a lymph node through the fibrous capsule and into the surrounding connective tissue] in the surgical specimen), will receive RT plus concurrent cisplatin (3 cycles of 100 mg/m 2 Q3W) plus pembrolizumab (15 cycles of 200 mg Q3W) in the pembrolizumab arm (Arm A) and without pembrolizumab in the SoC arm (Arm B); participants considered lower risk for recurrence (ie, without positive margins or extranodal extension following surgical resection) will receive RT plus pembrolizumab (15 cycles of 200 mg Q3W) in the pembrolizumab arm (Arm A) and without pembrolizumab in the SoC arm (Arm B). Participants in the pembrolizumab arm may start pembrolizumab adjuvant treatment before starting RT \pm cisplatin.

Participants who do not undergo surgical resection as originally planned, or have incomplete resection (ie, gross disease left behind) may receive salvage RT plus cisplatin \pm pembrolizumab, depending on the assigned treatment arm. These participants may receive a total dose of RT up to 70 Gy and up to 3 cycles of cisplatin.

All participants will have post-RT imaging performed 12 weeks (± 7 days) after the end of RT \pm cisplatin treatment and then every 3 months (91 ± 7 days) until the end of Year 3, the imaging schedule may then be reduced to every 6 months (182 ± 14 days) up to the end of Year 5. If an unplanned imaging assessment is performed before the first scheduled post-RT imaging and a disease progression is assessed per RECIST 1.1 and verified by BICR, this will be an EFS event. Participants who do not undergo the planned surgery, for whatever reason, will be followed by imaging assessments at the same time intervals from last dose of post-operative radiotherapy. Imaging scans will be performed until a primary efficacy endpoint event is observed for a participant (see Section 10.4 Analysis Endpoint for the definition of a primary efficacy analysis event).

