8 DISCONTINUATION/WITHDRAWAL CRITERIA

8.1 Discontinuation of Study Treatment

Discontinuation of study treatment does not represent withdrawal from the study.

As certain data on clinical events beyond study treatment discontinuation may be important to the study, they must be collected through the participant's last scheduled follow-up, even if the participant has discontinued study treatment. Therefore, all participants who discontinue study treatment prior to completion of the protocol-specified treatment period will still continue to participate in the study as specified in Section 2 - Schedule of Activities and Section 9.1.11 – Withdrawal/Discontinuation.

Participants may discontinue study treatment at any time for any reason or be dropped from the study treatment at the discretion of the investigator should any untoward effect occur. In addition, a participant may be discontinued from study treatment by the investigator or the Sponsor if study treatment is inappropriate, the trial plan is violated, or for administrative and/or other safety reasons. Specific details regarding procedures to be performed at study treatment discontinuation are provided in Section 9.1.11 – Withdrawal/Discontinuation.

A participant must be discontinued from study treatment but continue to be monitored in the study for any of the following reasons:

- The participant or participant's legally acceptable representative requests to discontinue study treatment.
- The participant has a medical condition or personal circumstance, which, in the opinion of the investigator and/or Sponsor, placed the participant at unnecessary risk from continued administration of study treatment.
- The participant has a confirmed positive serum pregnancy test.
- BICR verified radiographic disease progression outlined in Section 9.2.1.4.
 - Exceptions:
 - Participants with no histologic evidence of invasive cancer after definitive biopsy of the progressed lesion will not meet criteria for an event.
 - Radiographic disease progression during the neoadjuvant phase that precludes surgery will be considered an event.
- Any progression or recurrence of any malignancy, or any occurrence of another malignancy that requires active treatment.
- Recurrent Grade 2 pneumonitis.
- Completion of 17 doses of treatments with pembrolizumab.

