9.2.1.3 End of Treatment and Follow-up Tumor Imaging

For participants who discontinue study treatment without a documented event/disease progression, every effort should be made to continue monitoring their disease status by tumor imaging using the same imaging schedule used while on treatment (every 3 months [91 \pm 7 days] until the end of Year 3, thereafter every 6 months [182 \pm 14 days] until the end of Year 5) to monitor disease status until an event/disease progression, pregnancy, death, withdrawal of consent, or the end of the study, whichever occurs first. For participants who discontinue study treatment due to an event/document disease progression, this is the final required tumor imaging.

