10.4.1 Efficacy Endpoints

10.4.1.1 Primary Efficacy Endpoint

- **Event-free survival (EFS):** the time from randomization to the first of the following events:
 - Radiographic disease progression per RECIST 1.1.
Exception:
 - Participants who undergo a definitive biopsy of the progressed lesion and are found to have no histologic evidence of invasive cancer will not meet criteria for an event.
 - Radiographic disease progression during neoadjuvant phase that precludes surgery will be considered an event.
 - Local or distant progression or recurrence (as assessed with imaging or biopsy as indicated).
 - Death due to any cause.

A secondary malignancy is not considered an EFS event.

See Section 10.6.1 for definition of censoring.

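### Required scans end on triggers wider than the EFS event definition, so a participant with BICR-verified but biopsy-negative progression could lose scheduled imaging while still at risk

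*Combined protocol and SAP*

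**What the plan says.** Section 10.4.1.1 counts radiographic progression as an EFS event but makes an exception: participants who have a definitive biopsy of the progressed lesion and "are found to have no histologic evidence of invasive cancer will not meet criteria for an event".

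Two places tie the end of imaging to that definition. Section 5.1 states: "Imaging scans will be performed until a primary efficacy endpoint event is observed for a participant", with a pointer to Section 10.4. The Synopsis (Duration of Participation) runs post-treatment imaging to an event, progression or recurrence, and cites Section 10.4.1.1 for what that means.

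The sections that direct follow-up use other triggers:

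- Section 9.10.3.4: participants who "experience an event or disease progression/recurrence verified by BICR will move into the Survival Follow-up Phase". Contact there is by telephone every 3 months.
- Section 9.10.4: "Participants that discontinue study treatment due to an event/disease progression/recurrence will enter Safety Follow-up and then proceed directly to Survival Follow-up", with a reference to Section 8.1.
- Section 9.2.1.3: "For participants who discontinue study treatment due to an event/document disease progression, this is the final required tumor imaging".
- Schedule of Activities 2.4, footnote a: imaging continues until an event or disease progression, with no exception stated.

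In Survival Follow-up there is no scan calendar. Schedule of Activities 2.4 asks sites to collect "imaging assessment/biopsies performed as part of SOC to evaluate disease status for participants in survival follow-up who have not yet experienced an event/progression".

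Section 8.1 lists BICR-verified progression as a reason to discontinue treatment and repeats the biopsy exception under that bullet. The next bullet reads: "Any progression or recurrence of any malignancy, or any occurrence of another malignancy that requires active treatment". It carries neither a BICR qualifier nor an exception.

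**The concern.** The rule that stops scans should match the rule that defines the primary endpoint. If scans stop on something broader, some participants remain at risk for EFS with no scheduled way of having an event detected. Section 10.6.1.1 censors participants without an event at their last disease assessment. For these participants that could be the assessment that raised suspicion, so censoring may be related to prognosis.

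The exposure may also differ by arm. Sections 9.2.1.3 and 9.10.4 act on participants who discontinue study treatment because of progression. Arm B finishes study treatment with RT ± cisplatin, before its first scheduled post-RT scan 12 weeks later. Arm A is scanned while adjuvant pembrolizumab continues. That route therefore falls mainly on Arm A. The trigger in Section 9.10.3.4 applies to both arms.

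**Working it through.** **Comparing the triggers.** No figure in the plan can be reproduced here: the event counts, power and efficacy bounds are redacted. The check sets each trigger against two cases that are not EFS events.

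| Place | Trigger | BICR-verified, biopsy-negative | Site-called, not BICR-verified |
|---|---|---|---|
| 5.1 | Primary endpoint event | Scans continue | Scans continue |
| Synopsis | Event, progression or recurrence per 10.4.1.1 | Scans continue | Scans continue |
| 9.10.3.4 | Event, or BICR-verified progression | Scheduled scans end | Not triggered |
| 9.10.4 and 9.2.1.3 | Discontinuation due to event or progression | End, unless the 8.1 exception prevents discontinuation | End only if the unqualified 8.1 bullet is applied |
| SoA 2.4, footnote a | Event or disease progression | End on a literal reading | Unclear |

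The clear case is biopsy-negative progression under Section 9.10.3.4: its wording makes BICR-verified progression a trigger alongside an event and has no exception. If the biopsy result arrives after treatment has been stopped, no passage explicitly returns the participant to the scan calendar.

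The secondary case is the unqualified bullet in Section 8.1. Sections 9.2.1 and 9.2.1.2 continue treatment until progression is verified, and 9.2.1.2 requires each later scan to be submitted until BICR verifies it. The 8.1 bullet can be read the other way. These passages must be reconciled.

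**Illustration of size.** The simulation used 714 participants allocated 1:1 (714 / 2 = 357 per arm) and 1,500 simulated trials per scenario. Assumed, not from the documents: control median EFS 30 months, hazard ratio 0.75, follow-up 24 to 60 months, scans stopping at 1.5 months in affected participants, and a median of 12 months from progression to death. After scans stop, only death counts. A participant who does not die is censored at 1.5 months. The event hazard in affected participants is either unchanged (×1) or tripled (×3).

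| Affected | Hazard | HR, scans kept | HR, scans stopped | Ratio | Events lost |
|---|---|---|---|---|---|
| 2% of Arm A (0.02 × 357 ≈ 7) | ×1 | 0.752 | 0.757 | 1.007 | 1.2 |
| 2% of Arm A | ×3 | 0.762 | 0.756 | 0.992 | 1.6 |
| 5% of Arm A (0.05 × 357 ≈ 18) | ×1 | 0.747 | 0.761 | 1.018 | 3.0 |
| 5% of Arm A | ×3 | 0.793 | 0.778 | 0.981 | 4.2 |
| 10% of Arm A (0.10 × 357 ≈ 36) | ×1 | 0.745 | 0.773 | 1.038 | 6.0 |
| 10% of Arm A | ×3 | 0.836 | 0.807 | 0.965 | 8.3 |
| 5% of both arms | ×1 | 0.750 | 0.751 | 1.002 | 6.4 |
| 5% of both arms | ×3 | 0.754 | 0.754 | 1.000 | 8.1 |

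Total events were about 400 (399 to 412). Stopping scans removes events, which flatters the affected arm, and removes event-free time, which penalizes it. The net direction depends on the hazard in those affected.

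The stop at 1.5 months is early. In Arm A, with surgery at week 6, RT starting 6 weeks later and lasting 6 weeks, and a scan 12 weeks after that, the first scheduled post-RT scan falls at 6 + 6 + 6 + 12 = 30 weeks. The illustration therefore removes more follow-up per participant than a stop at that scan would.

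**The case against.** The strongest reply is that the intended rule can be recovered from the documents. Section 5.1 is explicit, and the Synopsis ties the compound phrase to Section 10.4.1.1. Section 9.10.4 refers to Section 8.1, where the biopsy exception is repeated. This stands, and it makes the point a contradiction rather than a settled decision to stop scans. It does not remove the point: Section 9.10.3.4 and the Schedule of Activities are what a site follows, and neither carries the exception.

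The second reply is that outcome information still arrives. Deaths always count, and documented events count in the primary analysis despite missed visits or new therapy (Section 10.6.1.1, Table 13). Standard-of-care images and biopsies are collected or requested (Schedule of Activities 2.4, Sections 9.1.7 and 9.10.3.3). An investigator-assessed EFS sensitivity analysis is planned, which speaks to site calls that BICR did not verify. This also largely stands. However, standard-of-care imaging follows no protocol schedule. Its collection in Schedule of Activities 2.4 is also limited to participants without an event or progression, which repeats the same ambiguity. The sensitivity analysis cannot restore scans that were not done.

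A reader might infer that presurgical progression that does not preclude surgery also ends scheduled scans, and that tumor flare would concentrate this in Arm A. The documents do not support that. Section 9.2.1.2 limits neoadjuvant discontinuation to progression that precludes surgery, Section 9.10.3.4 sits under post-treatment visits, and Section 5.1 gives all participants post-RT imaging. Flare is mentioned only for the presurgery scan, where Section 9.2.1.2 says it should not alter the decision to operate unless the tumor is unresectable.

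**Conclusion.** The inconsistency is real and worth correcting. BICR-verified, biopsy-negative progression is the clear case. The unqualified bullet in Section 8.1 is a secondary ambiguity.

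A reader might go further and conclude that EFS is informatively censored, or put a percentage on the participants lost. Neither follows. The documents give no number of progression calls, no rate of disagreement between site and BICR, and no rate of negative biopsies. Informative censoring is a possible consequence of one literal reading.

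The effect is probably small. In the illustration, with 2% to 5% of Arm A affected, the hazard ratio changes by a factor of 0.981 to 1.018; with 5% of both arms affected, by 1.000 to 1.002. These figures rest wholly on assumed inputs, and the direction is undetermined.

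**What to change.** Use one imaging-stop trigger, *an EFS event as defined in Section 10.4.1.1*, in Sections 9.2.1.3, 9.10.3.3, 9.10.3.4 and 9.10.4 and in Schedule of Activities 2.4, consistent with Section 5.1. Add a sentence that participants whose progression is not verified by BICR, or is overturned by biopsy, stay on the scheduled scan calendar whether or not study treatment has stopped. Reconcile the unqualified bullet in Section 8.1 with Sections 9.2.1 and 9.2.1.2. The survival contacts in Section 9.1.7 need no change.

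The cost is protocol wording, a site memo and a few scheduled scans that Section 5.1 already calls for. No endpoint, censoring rule or sample size changes.
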